5.4 Dispensing of the Investigational Product

DDFPe will be stored as detailed in [Section 5.2](#). A written order signed by one of the principal investigators must be obtained prior to dispensing.

5.5 Administration of the Investigational Product

For each cohort, the dose of DDFPe or placebo will be calculated based on body weight according to the table in [Appendix 2](#). Before administration, the drug will be prepared for injection per instructions in the Pharmacy Manual. DDFPe will be administered intravenously over 5-10 minutes through an IV catheter placed in a peripheral vein or through a central venous catheter (Note: a central venous catheter will not be placed solely for the study). The site of the intravenous catheter through which the study drug is administered will be recorded in the research record. Doses will be administered by slow IV push. After the first dose, subsequent doses will be administered 90 ± 10 minutes after the end of the previous infusion. Administration of all doses should occur with the syringe in the vertical position assuring that any

product foaming in the syringe will float near the rubber seal of the syringe plunger (NOTE: THIS IS THE MOST CRITICAL SAFETY CONSIDERATION DURING INFUSION). The placebo will be placed in identical syringes and administered in the same way. The volume of drug product to be used from each syringe will be provided on the label from pharmacy. The start and stop times for each infusion will be recorded on the source documents. The volume of the infusion will also be recorded.

5.6 Prior and Concomitant Therapy

5.6.1 Excluded Drug Therapy Prior to Enrollment

Blood clot lysing agents normally used in patients with non-hemorrhagic stroke may be used as indicated for acute treatment of AIS. Acute or chronic dosing with the following medications precludes entry into the study:

- Anticoagulants with the exception of low dose aspirin, prophylactic doses of low molecular weight heparin and warfarin
- All non-prescription medications and herbal remedies must be reviewed and approved by the investigator.
- NSAIDs are permissible.

5.6.2 Prohibited Drug Therapy During and 24 Hours after the Administration of the Investigational Product

The following drugs are not allowable within 24 hours after the last dose of DDFPe:

- None

5.6.3 Criteria for Stopping the Investigational Product

The investigational agent will be discontinued in the event that:

- Life-threatening disease progression occurs
- Unacceptable adverse events
- Subject wishes to withdraw from the study
- Changes in the patient's condition that, in the opinion of the investigator, present unacceptable risk to the subject

5.7 Return and Destruction of the Investigational Product

Any doses of DDFPe or placebo that are dispensed but not administered to an individual subject will be returned to the Pharmacy, documented in the drug accountability record, and handled as per Section 5.5. Any DDFPe or placebo that remains at the end of the study will be entered into the drug accountability records and returned to NuvOx or destroyed (21 CFR 312.62). Destruction will be witnessed and recorded appropriately.

6.0 **Study Subjects**

6.1 Study Population

The study population will include any male or female patients, ages 18years old or older, who present to UAMS with evidence of an AIS. The potential subjects must have a CT scan demonstrating that there is no evidence of hemorrhage or major

trauma. Potential subjects must not have had recent (within 3 months) intracranial surgery. Subjects must meet all of the inclusion and exclusion criteria prior to enrollment. The patient or a legally authorized representative must be able and willing to provide informed consent.

6.2 Inclusion Criteria

6.2.1 Ages 18 years old or older

6.2.2 Diagnosis of AIS

6.2.3 Body weight \geq 45 kg

6.2.4 NIHSS between 2 and 20 inclusive.

6.2.5 Patient or LAR must be willing and able to understand the study and provide written informed consent

6.3 Exclusion Criteria

6.3.1 Currently pregnant or breastfeeding

6.3.2 History of significantly impaired renal or hepatic function

6.3.3 Severe hemorrhage or severe hemorrhagic stroke on CT scan. Mild or moderate changes of Fisher Grade 1 or 2 subarachnoid hemorrhage are allowed as are hemorrhagic transformation changes of Grade HI-1 and HI-2^{24,25}.

6.3.4 Prior stroke, intracranial surgery, or major head trauma within three (3) months prior to enrollment

6.3.5 Pre-stroke mRS \geq 2 (See [Appendix 3](#))

6.3.6 Myocardial infarction within six (6) months prior to enrollment

6.3.7 Unstable angina, NYHA Class II or greater congestive heart failure

6.3.8 Uncontrolled hypertension (SBP > 180 and/or DBP > 110 mmHg)

6.3.9 Uncontrolled arrhythmia or history of clinically significant arrhythmia within the past six (6) months (except atrial fibrillation)

6.3.10 Clinically significant COPD or other pulmonary condition that is not controlled by medication or requires oxygen frequently or continuously

6.3.11 Pneumonia, bronchitis, or other acute respiratory disease

6.3.12 Current anticoagulant therapy except for antiplatelet therapy (aspirin, NSAIDs) and prophylactic doses of low molecular weight heparin to prevent deep vein thrombosis. Note: tPA administered as part of subjects' therapy for AIS is allowed. However, thrombolytic therapy is not a study requirement.

6.3.13 History of allergic reaction attributed to compounds of similar chemical composition to DDFPe or soy or egg allergies (see Investigator's Brochure).

6.3.14 Subject has received any investigational drug within thirty (30) days prior to enrollment into the study

6.3.15 Inability to comply with the study procedures

6.3.16 History or evidence of any other clinically significant condition that, in the opinion of the investigator, might pose a safety risk to subjects or interfere with study procedures, evaluation, or completion

6.4 Withdrawal Criteria

Subjects may choose to withdraw from the study at any time for any reason. Additionally, the investigator may choose to remove subjects from the study. Any subject withdrawing their consent to participate in the study or their authorization to use their protected health information will be withdrawn from the study.

Subjects will be informed that the investigational product may be discontinued by the investigator even if the subject and/or the LAR wish to continue. This may occur for the following reasons:

- Serious Adverse Event (SAE) believed to be related to investigational product
- Intolerable side effects
- Failure to complete required study procedures
- Clinically significant laboratory or ECG abnormalities
- Significant change in oxygenation as measured by pulse oximetry
- Initiation of treatment with a prohibited drug during the intervention phase
- Non-compliance with the treatment regimen

Subjects may also be withdrawn for any reason if the investigator believes that it is in the best interest of the subject to discontinue the study.

6.5 Replacement of Subjects

Subjects who withdraw or are withdrawn from the study prior to the completion of the Day 7 visit may be replaced at the discretion of the investigator.

7.0 **Investigational Plan**

7.1 Usual Care Provided by Treating Physician

Customary (routine) care for patients suffering a stroke will be offered as would be the case had the patient not enrolled in the trial. This may include physiological monitoring, medical procedures, drug therapy (including tPA), respiratory support, and ancillary or accessory care. Routine care will be directed by the patient's treating physician. If the treating physician believes that it is no longer in the best interest for the patient to continue in the study, he/she will contact the investigator and immediately stop all study-related procedures.

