5.3.2 Dose Limiting Toxicity

Dose limiting toxicity (DLT) will be defined by the following criteria:

- Clinically significant changes in vital signs:
 - Heart rate \pm 50% from baseline
 - Respiratory rate >30 /min
 - Systolic blood pressure < 90 mmHg or >220 mmHg
 - Diastolic blood pressure >110 mmHg
- New (i.e. not seen at baseline) ECG changes consistent with:
 - Acute right ventricular dilation or strain
 - Incomplete or complete bundle branch block
 - Q waves in leads III and aVF
 - T-wave inversion and/or ST segment changes in the precordial leads
 - Any other clinically significant cardiac arrhythmia
- Common Terminology Criteria for Adverse Events (CTCAE) 4 Grade 3 or higher cough, dyspnea, chest pain-cardiac or non-cardiac, chest wall pain or hypoxia (See [Appendix 1](#) for specific criteria)
- NIHSS: sudden worsening of 4 or more from the baseline (pre-DDFPe initiation)
- The Medical Monitor will review all data collected at Post-Dose #3 (approximately 4-6 hours after the end of the Dose #3 infusion of DDFPe or placebo for each subject). Enrollment will be on hold until the Medical Monitor has reviewed the data and approves enrollment of an additional subject. The Medical Monitor may choose to temporarily halt the study if serious concerns arise regarding subject safety.

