7.3 Verification of Inclusion/Exclusion Criteria

After the consent process is complete, trained study personnel will review the Inclusion and Exclusion criteria with the subject/LAR. The following options are then possible:

- If the subject meets all criteria, they will be allowed to proceed with the study.
- If the subject fails to meet criteria, no further study-related procedures will be conducted.
- If the failure to meet criteria is minor, the investigator may choose to approach the Medical Monitor for a waiver. A waiver will be granted only if doing so will not place the subject at increased risk if allowed to participate in the study.

Study personnel will document the review of Inclusion and Exclusion Criteria on the appropriate form and place the signed form in the study file. The investigator will be notified of the results of the review.

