7.7 Day 4: Study Procedures

All subjects will be contacted to assess AEs. If the subject is still hospitalized, any significant change in condition will be recorded as a possible AE and assessed by the investigator. All AEs will be graded (mild, moderate, severe), assessed for relatedness (not related, possibly related, probably related, definitely related), and followed to resolution as described in Section 8.0.

In the event that the subject has been discharged from the hospital before Day 4, subjects or their LAR will be contacted by telephone. AEs will be assessed and followed as described above.

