7.9 Day 30 (±7 days): Study Procedures or Telephone Follow Up

This visit will occur as part of the routine, clinically indicated follow up. If no routine appointment is scheduled, the subject may be contacted by telephone to complete the study visit. At this visit, the following procedures will occur:

- Interval medical history
- A brief physical examination (omitted for telephone follow up)
- Vital signs (BP, HR, RR) (omitted for telephone follow up)
- mRS
- NIHSS (omitted for telephone follow up)
- Adverse Events

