8.0 Adverse Events

8.1 Definitions

Adverse Event

An adverse event (AE) is any untoward medical occurrence that develops or worsens in severity during the course of the study, whether or not it has a causal relationship to the study treatment. Concurrent illnesses or injuries should be regarded as AEs. Abnormal results of diagnostic procedures are considered AEs if the abnormality:

- results in study withdrawal
- is associated with a serious adverse event
- is associated with clinical signs or symptoms
- leads to additional treatment or to further diagnostic tests
- is considered by the investigator to be of clinical significance

Serious Adverse Event

Adverse events are classified as serious or non-serious. A *serious adverse event (SAE)* is any AE that is:

- fatal
- life-threatening
- requires or prolongs hospital stay
- results in persistent or significant disability or incapacity
- a congenital anomaly or birth defect
- an important medical event

Important medical events are those that may not be immediately life threatening, but are clearly of major clinical significance. They may jeopardize the subject, and may require intervention to prevent one of the other serious outcomes noted above. For example, drug overdose or abuse, a seizure that did not result in in-patient hospitalization or intensive treatment of bronchospasm in an emergency department would typically be considered serious.

All adverse events that do not meet any of the criteria for serious should be regarded as *non-serious adverse events*.

Adverse Event Reporting Period

The study period during which adverse events must be reported is normally defined as the period from the initiation of any study procedures to the end of the study treatment follow-up. For this study, the study treatment follow-up is defined as within 90 days following the last administration of study treatment.

Preexisting Condition

A preexisting condition is one that is present at the start of the study. A preexisting condition should be recorded as an adverse event if the frequency, intensity, or the character of the condition worsens during the study period (e.g. if behavior worsens).

General Physical Examination Findings

At screening, any clinically significant abnormality should be recorded as a preexisting condition. At the end of the study, any new clinically significant findings/abnormalities that meet the definition of an adverse event must also be recorded and documented as an AE.

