8.2 Recording of Adverse Events

At each contact with the subject, the investigator must seek information on adverse events by specific questioning and, as appropriate, by examination. Information on all AEs should be recorded immediately in the source document, and also in the appropriate adverse event module of the case report form (CRF). All clearly related signs, symptoms, and abnormal diagnostic procedures results should be recorded in the source document and grouped under one diagnosis when possible.

All AEs occurring during the study period must be recorded. The clinical course of each event should be followed until resolution, stabilization, or until it has been determined that the study treatment or participation is not the cause. Serious adverse events that are still ongoing at the end of the study period must be followed up to determine the final outcome.

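### A treating-physician stop under Section 7.1 ends all study procedures, not just study drug, so DLT criteria can go unassessed in a dosed subject who may then be replaced

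*Combined protocol and SAP*

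**What the plan says.** Section 7.1 covers usual care. If the treating physician thinks the patient should no longer continue, "he/she will contact the investigator and immediately stop all study-related procedures". It makes no exception for safety follow-up. Section 5.6.3, by contrast, lists reasons for discontinuing the investigational agent only.

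The DLT definition in Section 5.3.2 includes "New (i.e. not seen at baseline) ECG changes consistent with" several listed patterns, and a sudden NIHSS worsening of 4 or more points from baseline. It also has vital-sign limits and selected CTCAE Grade 3 events. Section 7.6 and Appendix 4 schedule the ECG, NIHSS and laboratory tests that feed this assessment.

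Section 5.3.3 lets subjects be replaced if they withdraw for a reason other than a DLT. Section 6.5 leaves replacement before completion of the Day 7 visit to the investigator's discretion.

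On adverse events, Section 8.1 states that "the study treatment follow-up is defined as within 90 days following the last administration of study treatment", and Section 8.2 that "All AEs occurring during the study period must be recorded". Section 7.7 says of Day 4: "All subjects will be contacted to assess AEs".

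On oversight, Section 5.3.2 says "Enrollment will be on hold until the Medical Monitor has reviewed the data and approves enrollment of an additional subject". Section 5.3.3 separately requires the Medical Monitor to review each patient's safety data and approve the next patient and cohort.

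**The concern.** DLT is the primary outcome and drives the MTD decision; adverse-event frequency and severity is the secondary objective. A 7.1 stop is unlikely to be random with respect to either, since it happens because a physician is worried about the patient. A rule that ends safety measurement at that moment loses data where they are most informative. If the stopped subject has no DLT on record because the ECG or NIHSS was never taken, the subject can look like a withdrawal unrelated to toxicity and be replaced. The count that decides escalation would then be too low. The loss would come from following the protocol as written, not from a lapse in conduct.

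**Working it through.** **1. Which readings a literal stop cancels.** Appendix 4 and Sections 7.6, 7.8 and 7.9 schedule these post-dose readings:

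- ECG: Post-Dose #3 and Day 7/discharge (2).
- Laboratory tests: the same two times (2).
- NIHSS: after Dose #2, after Dose #3, Post-Dose #3, Day 7/discharge and Day 30 (5; the last is omitted if follow-up is by telephone).

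Readings already taken when the stop occurs:

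| Time of stop | ECG | NIHSS | Labs |
|---|---|---|---|
| After Dose #1, before the Dose #2 NIHSS | 0 of 2 | 0 of 5 | 0 of 2 |
| After the Dose #2 NIHSS, before the Dose #3 NIHSS | 0 of 2 | 1 of 5 | 0 of 2 |
| After the Dose #3 NIHSS, before Post-Dose #3 | 0 of 2 | 2 of 5 | 0 of 2 |
| After Post-Dose #3, before Day 7/discharge | 1 of 2 | 3 of 5 | 1 of 2 |

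Any stop before Post-Dose #3 leaves the ECG criterion with no scheduled post-dose reading. A stop before the Dose #2 NIHSS does the same for the NIHSS criterion. Section 5.3.2 has no laboratory criterion, but the Study Summary names laboratory values among the primary outcome measures. Vital signs and oximetry are less exposed, because they are recorded every 15 minutes up to the stop.

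**2. What happens to that subject in the MTD algorithm.** Section 5.3.3 counts subjects with a DLT. It does not say how to classify a dosed subject who lacks the Post-Dose #3 data. Section 7.1 does not say whether a stopped subject counts as withdrawn, but Section 6.4 permits withdrawal in the subject's best interest, which would open the replacement route.

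**3. Adverse-event collection.** Several places label it a study procedure: Section 7.7 is titled as study procedures and contains only adverse-event contact; Sections 7.9 and 7.10 list adverse events under "At this visit, the following procedures will occur"; Appendix 4 lists them in its study-procedures column. Against this, Sections 8.1 and 8.2 set a 90-day period and a recording duty with no exemption for stopped subjects. No clause ranks 7.1 against Section 8. The duty in 8.1 to follow unresolved events covers those that began before the stop, not new ones.

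**4. Size: illustration only.** The plan gives no figure to reproduce; Section 10.1 says no sample size estimate was made. The DLT rate p and the share u of DLTs left unobserved are assumptions. Let X be the number of DDFPe subjects with an observed DLT, X ~ Binomial(6, q). The MTD is exceeded if X ≥ 3.

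- One missed DLT changes the result only if exactly three of six have one: P(X = 3) = 20p³(1−p)³ = 0.185, 0.276 and 0.312 for p = 0.30, 0.40 and 0.50.
- With full observation (q = p): P(X ≥ 3) = 0.256, 0.456 and 0.656.
- If each subject with an unobserved DLT is replaced, q = p(1−u)/(1−pu). For u = 0.05: 0.236, 0.430 and 0.632. For u = 0.10: 0.217, 0.404 and 0.606. The fall is about 2 to 5 percentage points.
- Without replacement, q = p(1−u). For u = 0.05: 0.228, 0.414 and 0.608. For u = 0.10: 0.202, 0.373 and 0.558. The fall is about 3 to 10 points.

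**The case against.** The strongest reply is that 7.1 instructs the treating physician, in a section on usual care, while Section 8 binds the investigator without condition. A reader might infer from 7.1 that adverse-event collection ends at the stop and that the protocol contradicts itself. The documents do not support that. The phrase in 7.1 is undefined, and a column label in a schedule is not a definition. Section 8.1 anchors the 90 days to the last dose rather than to continued participation, and Section 7.7 covers all subjects. Section 7.3 does use similar words to end study activity ("If the subject fails to meet criteria, no further study-related procedures will be conducted"), but for screen failures, who were never dosed. Days 30 and 90 are also tied to routine follow-up. This part of the reply stands: what remains is an unstated precedence, not a contradiction.

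A second reply is that the Medical Monitor already controls the risk. A replacement is a next patient, so the Monitor must review the stopped subject first, and the requirement in 5.3.3 is not limited to Post-Dose #3 data. Section 5.3.2 does not restrict DLTs to scheduled readings, so a change seen in usual care still counts. This also stands, and it reduces the effect. But the Monitor can review only what was measured, no ECG or NIHSS is guaranteed after the stop, and no rule classifies the case.

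A third reply is that the thin ECG and NIHSS schedule is the real cause, and that a consent withdrawal would have the same result. That is partly true. A withdrawal of consent has to be respected, however, whereas the breadth of 7.1 is the protocol's own choice.

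**Conclusion.** The concern holds for the DLT and safety assessments. They are plainly study procedures, 7.1 stops all of them, and a dosed subject may lack an ECG, an NIHSS score or both when DLT status is judged and replacement is considered. For adverse events to Day 90 it holds only as an ambiguity; the sensible reading keeps collection going.

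The size cannot be estimated from the documents. A reader might take the illustrative falls as the expected loss of protection. They are not: p and u are assumed, the documents support no particular value of u, and the upper end of 10 points needs p = 0.50, u = 0.10 and no replacement. The figures also concern missed DLTs only and say nothing about lost adverse events. Nor does a missed DLT by itself cause escalation, which still needs the Medical Monitor's approval. The case for change rests on the wording and its low cost. It should be made, but it does not undermine the design.

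**What to change.** In Section 7.1, replace the instruction to stop all study-related procedures with: *immediately stop further study drug; unless the subject or LAR withdraws consent, AE follow-up to Day 90 and the remaining scheduled safety assessments (vital signs, ECG, NIHSS, labs) continue, except any specific assessment the treating physician judges not to be in the patient's best interest, which is omitted and documented*. The exception settles which side prevails if the physician objects to an assessment, and the physician's threshold for stopping is unchanged.

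In Sections 5.3.3 and 6.5, add: *a dosed subject stopped under Section 7.1 is replaced only after the Medical Monitor has classified DLT status from all available data*.

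The cost is these two short wording changes, with the amendment approvals in Section 11.5, and minor follow-up burden in a few subjects. Day 4 contact after discharge and the Day 30 and Day 90 contacts may already be by telephone. The consent form is not in the supplied text, so whether it needs a matching change cannot be checked.

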7.2 Consent Process

Potential study subjects whose condition has rendered them unable to provide informed consent due to aphasia, confusion, impaired consciousness or other cognitive impairments such as intellectual disability and dementia will require a legally authorized representative (LAR).

Trained study personnel will review the IRB-approved study summary brochure with the subject/LAR and answer questions followed by reviewing the informed consent document with the subject and/or a LAR. The subject/LAR will be allowed to ask questions. If the subject/LAR agrees to participate, the consent will be signed and a copy will be provided to the subject. Once the consent process is complete, study

personnel will document the process in a note to be placed in the study file along with the signed consent document.

All screened and enrolled subjects will be recorded in the Screening and Enrollment Log at each participating institution. All enrolled subjects should be reported to [name] within 24 hours using the Study Participant Registration form. [name] will advise all PIs as to when it is acceptable to proceed with the next subject. All pre-determined stopping points will be observed (i.e. after each subject in each cohort and at the end of each cohort prior to proceeding to the next highest dose).

